#### 5.3.2.2 Ketone measurement

Patients will be equipped with an electronic device to determine their ketone concentration (i.e. a blood glucose monitoring device/meter that is also capable of measuring blood ketones).

Patients should be reminded to test their ketones in case of any symptoms of DKA, e.g. nausea, vomiting, abdominal pain etc., irrespective of the glucose value. Patients must be reminded about the signs and symptoms of DKA, on the interpretation of ketone values measured via the meter, and on appropriate action to take in the event of increased ketone levels (see below). In the same way as during routine clinical care, patients should also be reminded to test for ketones in case of repeatedly elevated blood glucose levels (e.g. > 200 - 240 mg/dL [> 11.1 - 13.3 mmol/L]) which cannot be explained. Regular (e.g. 2-3 times a week) measurements before breakfast are recommended throughout the trial from Visit 2. More frequent (e.g. once daily) measurements before breakfast are recommended during the run-in period and during the first 4 weeks of the treatment period and might also be agreed upon with the patient afterwards if deemed necessary by the Investigator.

In the event of increased ketones, patients should either follow the rules given by their Investigator (e.g. increased fluid intake and/or insulin bolus; food intake and insulin bolus in case of near-normal blood glucose) or contact their trial site. In case of deteriorating ketosis, blood glucose and ketone levels should be checked every 1-2 hours until they are back in a range considered to be normal for the patient. Patients should be instructed to immediately refer themselves to hospital and/or the Investigator, or to contact an emergency physician, in case of a blood ketone concentration > 1.5 mmol/L (as indicated in the meter manual). In

case of a suspected DKA the Investigator should ensure that appropriate tests are performed at the earliest opportunity according to local guidelines, such as a blood gas test (pH, bicarbonate). The results will be collected on the relevant page of the eCRF.

Investigators should also differentiate deteriorating ketosis/DKA from any mild to moderate increase of ketones which may be seen due to the mechanism of action of empagliflozin, especially in the fasted state (e.g. in the morning). For further details, see also Sections 1.2.3.2 and 2.3.

In accordance with Section 3.3.2, Investigator's should carefully select patients for the study in terms of their ability to comply with ketone measurement requirements. Patients not adhering to the instructions given by the Investigator should be retrained at the earliest possible opportunity.

# 5.3.3 Safety laboratory parameters

At the following visits, laboratory samples will be collected from the patient after a full overnight fast (i.e. nothing to eat or drink except water for at least 10 hours): Visits 2, 6, 9, 12, 14, 16, eEOT (if applicable), and 17. At all other visits, the patient does not have to be in a fasted state when laboratory samples are taken.

When applicable, laboratory samples, as described in the Flow Chart, should be collected before trial medication is taken.

All parameters that will be determined during the trial conduct are listed in Table 5.3.3: 1 and Table 5.3.3: 2. The analysis will be performed by a central laboratory. The respective reference ranges and details about sample handling and shipment will be provided in the laboratory manual in the ISF.

UACR in spot urine will be calculated at the central laboratory.

The central laboratory will derive the eGFR from (and report it together with) serum creatinine values based on the CKD-EPI formula which is considered more accurate in the normal range than the Modification of Diet in Renal Disease (MDRD) formula. The CKD-EPI formula will be defined in central laboratory documentation due to regional/racial variations in the formula that is applied.

The eGFR (cystatin C, serum) will also be derived, at the visits where cystatin C levels are measured.

# Table 5.3.3: 1 Safety laboratory parameters – blood, serum or plasma

# Haematology Haematocrit Haemoglobin o retici

- o reticulocyte count (reflex test if haemoglobin is outside normal range)
- Red blood cells (RBC)/erythrocytes
- White blood cells (WBC)/leukocytes
- Platelet count/thrombocytes
  - Differential automatic (relative and absolute count):
    - neutrophils, eosinophils, basophils, monocytes, lymphocytes

# **Clinical chemistry**

- Albumin
- Alkaline phosphatase
  - gamma-glutamyl transferase
     (γ-GT, reflex test triggered by
     elevated alkaline phosphatase
     on two sequential measures)
- ALT (alanine aminotransferase, SGPT)
- AST (aspartate aminotransferase, SGOT)
- Beta-hydroxy-butyrate
- Bicarbonate
- Bilirubin total, fractionated if elevated
- Calcium
- Chloride
- C-peptide
- Creatinine
- ,
  - -:...6

- Creatine kinase (CK)
  - o troponin I (reflex test if CK is elevated)
- Cystatin C
- Lactate dehydrogenase
- Lipase
- Magnesium
- Phosphate
- Potassium
- Protein total
- iPTH (intact parathyroid hormone)
- Sodium
- TSH
- Blood urea nitrogen (BUN)
- Uric acid

# $Lipids^6$

- Cholesterol (total)
- HDL cholesterol
- LDL cholesterol (calculated)
- Triglycerides
  - direct measurement of LDL cholesterol (reflex test if triglycerides are > 400 mg/dL or 4.52 mmol/L)
- At the screening visit (Visit 1), only the following parameters are part of the profile: liver transaminases, alkaline phosphatase, creatinine, and TSH
-  C-peptide will only be assessed at Visit 2
-  Cystatin C will only be assessed at Visits 6, 12, 16, eEOT (if applicable) and 17
- iPTH will be only be assessed at Visits 6, 8, 16 and eEOT (if applicable)
-  TSH will only be assessed at Visit 1
- 6 Lipids will only be assessed at Visits 6, 12, 16, eEOT (if applicable), and 17

Page 56 of 144

Proprietary confidential information © 2017 Boehringer Ingelheim International GmbH or one or more of its affiliated companies

Table 5.3.3: 2 Laboratory parameters – urine

	Semi-quantitative (dipstick) urinalysis	Quantitative urinalysis		
ŀ	• Nitrite 	• Albumin		
ŀ	• Protein	Creatinine		
ŀ	• Ketones	Human chorionic gonadotrophin		
ŀ	• Urine pH	(hCG) 		
ŀ	• Leukocyte esterase (for WBC) 			

# Microscopic urinalysis

Microscopic analysis will be performed as a reflex test if any of the above semiquantitative (dipstick) tests except for ketones are abnormal:

- Urine RBC/erythrocyte
- Urine WBC/leukocytes
- Urine sediment microscopic examination

#### Urine culture

Urine culture will be triggered by positive leukocyte esterase (for WBC) and/or nitrite in the semi-quantitative test/dipstick. The culture will include an antibiogram

- Nitrite and leukocyte esterase (for WBC) will be determined both locally on site (not recorded in eCRF) and via the central laboratory. A positive result at site triggers the sampling of mid-stream urine for urine culture
-  Urine pregnancy testing will be performed locally in female patients of child-bearing potential only according to the timepoints indicated in the Flow Chart

# 5.3.3.1 Follow-up on suspicion for urinary tract infections

Patients having a history of chronic/recurrent UTI or genital infection or an acute episode of UTI or genital infection at screening will be identified and this condition must be documented as medical history or as a baseline condition in the eCRF, respectively.

Throughout the trial, patients should be closely observed for symptoms of UTI or genital infection. In case these symptoms occur, symptomatic relief and anti-infectives should be provided as appropriate [c01678844].

For documentation of acute UTI during trial conduct, the following measures have to be taken:

- In any case of suspected UTI (symptomatic or asymptomatic) a urine culture sample has to be taken and sent to the central laboratory for confirmation of the diagnosis and to obtain an antibiogram
- To be able to identify asymptomatic UTIs immediately, a dipstick test (leukocyte esterase [for WBC] and nitrite) will be performed at the site at the timepoints indicated in the

Page 57 of 144

Proprietary confidential information © 2017 Boehringer Ingelheim International GmbH or one or more of its affiliated companies

Flow Chart. In case of a positive result at site, a urine culture sample must be obtained and sent to the central laboratory for confirmation of the diagnosis and to obtain an antibiogram

# 5.3.4 Electrocardiogram

Printed paper traces from 12-lead ECGs (I, II, III, aVR, aVL, aVF, V1-V6) will be collected at the timepoints indicated in the Flow Chart. In the event of any cardiac symptoms (i.e. suspicion of heart rhythm disorders or cardiac ischaemia), an additional ECG will be recorded. All ECGs will be evaluated, signed, dated and commented upon by the treating physician/Investigator and stored locally. Any clinically relevant changes in the ECG will be reported as AEs and followed up and/or treated locally until normal or stable condition.

# 5.3.5 Other safety parameters

# 5.3.5.1 Assessment of hypoglycaemia rate

Hypoglycaemia rates will be assessed based on AE data, which in turn rely on the criteria for hypoglycaemic events (see Section 5.3.5.2 below). Glucose values used within the criteria for hypoglycaemic events will originate in the SBGM device and from central laboratory measurements. All glucose values originating in the SGBM device will subsequently be entered into the e-diary (for further details please see Sections 5.2.3 and 5.3.2.1).

# 5.3.5.2 Criteria for hypoglycaemic events

Every episode of blood/plasma glucose  $\leq$  70 mg/dL ( $\leq$  3.9 mmol/L) should be documented with the respective time and date of occurrence. This includes hypoglycaemia with glucose values  $\leq$  54 mg/dL ( $\leq$  3.0 mmol/L) and all symptomatic and all severe hypoglycaemic events.

For the analysis, all hypoglycaemias will be classified according to the following criteria:

- Asymptomatic hypoglycaemia: event not accompanied by typical symptoms of hypoglycaemia but with a measured glucose concentration  $\leq 70 \text{ mg/dL}$  ( $\leq 3.9 \text{ mmol/L}$ )
- Documented symptomatic hypoglycaemia with glucose concentration ≥ 54 mg/dL and ≤ 70 mg/dL (≥ 3.0 mmol/L and ≤ 3.9 mmol/L): event accompanied by typical symptoms of hypoglycaemia
- Documented symptomatic hypoglycaemia with glucose concentration < 54 mg/dL (< 3.0 mmol/L): event accompanied by typical symptoms of hypoglycaemia but no need for external assistance
- Severe hypoglycaemia: event requiring the assistance of another person to actively administer carbohydrates, glucagon or take other corrective actions. Plasma glucose concentrations may not be available during an event, but neurological recovery following the return of plasma glucose to normal is considered sufficient evidence that the event was induced by a low plasma glucose concentration [R14-0982]

If a patient is provided with an emergency glucagon injection device as part of their local, routine T1DM care, it is advisable for the patient to carry this throughout the trial.

Page 58 of 144

Proprietary confidential information © 2017 Boehringer Ingelheim International GmbH or one or more of its affiliated companies

5.3.5.3 Assessment of cardiovascular events (CEC adjudication)

Please refer to Section 3.1.1.2.

5.3.5.4 Assessment of severe hypoglycaemia and DKA (CEC adjudication)

Please refer to Sections 3.1.1.3 and 5.3.5.2.

#### 5.3.6 Assessment of adverse events

5.3.6.1 Definitions of AEs

# **Adverse event**

An adverse event (AE) is defined as any untoward medical occurrence in a patient or clinical investigation subject administered a medicinal product and which does not necessarily have to have a causal relationship with this treatment.

An AE can therefore be any unfavourable and unintended sign (including an abnormal laboratory finding), symptom, or disease temporally associated with the use of a medicinal product, whether or not considered related to the medicinal product.

# Serious adverse event

A serious adverse event (SAE) is defined as any AE which:

- results in death
- is life-threatening
- requires inpatient hospitalisation or prolongation of existing hospitalisation
- results in persistent or significant disability or incapacity
- is a congenital anomaly/birth defect or
- is to be deemed serious for any other reason if it is an important medical event when based upon appropriate medical judgement which may jeopardise the patient and may require medical or surgical intervention to prevent one of the other outcomes listed in the above definitions.

Life-threatening in this context refers to an event in which the patient was at risk of death at the time of the event; it does not refer to an event that hypothetically might have caused death if more severe.

# AEs considered "Always Serious"

In accordance with the European Medicines Agency initiative on Important Medical Events, BI has set up a list of AEs, which by their nature, can always be considered to be "serious" even though they may not have met the criteria of an SAE as given above.

The latest list of "Always Serious AEs" can be found in the Remote Data Capture (RDC) system. These events should always be reported as SAEs as described in Section 5.3.7

#### **Adverse events of Special Interest (AESIs)**

The term AESI relates to any specific AE that has been identified at the project level as being of particular concern for prospective safety monitoring and safety assessment within this trial, e.g. the potential for AEs based on knowledge from other compounds in the same class. AESIs need to be reported to the Sponsor's Pharmacovigilance Department within the same timeframe that applies to SAE, see Section 5.3.7.

Patients with AESIs need to be followed up appropriately, regardless of the origin of the laboratory data (e.g. central, local etc.). The Investigator should consider which, if any, concomitant therapies should not be taken during evaluation. Discontinued treatments can be reintroduced per Investigator discretion.

The following are considered as AESIs:

# Hepatic injury

A hepatic injury is defined by the following alterations of hepatic laboratory parameters after randomisation (Visit 6):

- an elevation of AST and/or ALT  $\geq$  3 fold ULN combined with an elevation of total bilirubin  $\geq$  2 fold ULN measured in the same blood sample
- an isolated elevation of ALT and/or AST > 5 fold ULN

These laboratory findings constitute a hepatic injury alert and the patients showing these abnormalities need to be followed up according to the "DILI checklist" provided via the RDC-system.

In case of clinical symptoms of hepatic injury (icterus, unexplained encephalopathy, unexplained coagulopathy, right upper quadrant abdominal pain, etc.) without laboratory results (ALT, AST, total bilirubin) available, the Investigator should make sure these parameters are analysed, if necessary in an unscheduled blood test. Should the results meet the criteria of hepatic injury alert, the procedures described in the "DILI checklist" should be followed.

# Decreased renal function

Decreased renal function is defined by a creatinine value showing  $a \ge 2$  fold increase from baseline and is above the ULN.

For the AESI "decreased renal function" the Investigator shall collect an unscheduled laboratory sample for creatinine as soon as possible and initiate follow-up laboratory tests of creatinine according to medical judgement.

# Diabetic ketoacidosis (DKA)

DKA is defined by the diagnostic criteria in Table 5.3.6.1: 1 below, and as defined by the American Diabetes Association (ADA) [R14-5435].

Investigators should note that not all criteria in the table below need to apply for the diagnosis of DKA, and clinical judgement should also be taken into consideration. Due to its mechanism of action, empagliflozin may potentially modify the clinical presentation of DKA which may occur at lower plasma glucose levels than stated in Table 5.3.6.1: 1 below (see Sections 1.2.3.2 and 2.3 for further details).

Table 5.3.6.1: 1 Diagnostic criteria for DKA

	DKA		
	Mild	Moderate	Severe
Plasma glucose (mg/dL)	>250	>250	>250
Arterial pH	7.25-7.30	7.00-7.24	<7.00
Serum bicarbonate (mEq/L)	15-18	10 to <15	<10
Urine ketones*	Positive	Positive	Positive
Serum ketones*	Positive	Positive	Positive
Effective serum osmolality (mOsm/kg)**	Variable	Variable	Variable
Anion gap***	>10	>12	>12
Alteration in sensoria or mental obtundation	Alert	Alert/drowsy	Stupor/coma

\* Nitroprusside reaction method

# Severe hypoglycaemic episodes

Severe hypoglycaemic episodes are events requiring the assistance of another person to actively administer carbohydrate, glucagon or other corrective actions. Plasma glucose concentrations may not be available during an event, but neurological recovery following the return of plasma glucose to normal is considered sufficient evidence that the event was induced by a low plasma glucose concentration.

This includes fatal hypoglycaemic events.

# Events involving lower limb amputation

\*\* Calculation: 2[measured Na (mEq/L) + glucose (mg/dL)/18

\*\*\* Calculation:  $(Na+) - (Cl^2 + HCO3^2) (mEq/L)$ 

# c03024901-03 Trial Protocol Version 3.0

Page 61 of 144

Proprietary confidential information © 2017 Boehringer Ingelheim International GmbH or one or more of its affiliated companies

This definition includes amputation (i.e. resection of a limb through a bone), disarticulation (i.e. resection of a limb through a joint) and auto-amputations (i.e. spontaneous separation of non-viable portion of the lower limb).

Not included in this definition are debridement (removal of callus or dead tissue), procedures on a stump (like stump revision, drainage of an abscess, wound revision etc.) and other procedures (e.g. nail resection or removal) without a concomitant resection of a limb (amputation or disarticulation).

Each lower limb amputation, disarticulation, or auto-amputation should be reported separately. The SAE report should include the date of the procedure, the level of amputation or disarticulation, the medical condition(s) leading to the procedure and if the patient had some of the known risk factor(s) for lower limb amputation.

# **Intensity of AEs**

The intensity of the AE should be judged based on the following:

Mild: Awareness of sign(s) or symptom(s) that is/are easily tolerated Moderate: Enough discomfort to cause interference with usual activity

Severe: Incapacitating or causing inability to work or to perform usual activities

# **Causal relationship of AEs**

Medical judgement should be used to determine the relationship, considering all relevant factors, including pattern of reaction, temporal relationship, de-challenge or re-challenge, confounding factors such as concomitant medication, concomitant diseases and relevant history.

Yes: There is a reasonable causal relationship between the investigational product administered and the AE.

No: There is no reasonable causal relationship between the investigational product administered and the AE.

The causal relationship must be provided by the Investigator for all potential trial drugs, i.e. the BI trial drug and for all other trial drugs (such as any active comparator or placebo and for trial procedure).

# 5.3.7 Adverse event collection and reporting

#### **AE** collection

The following must be collected and documented on the appropriate eCRF and/or other designated data collection repository by the Investigator (see also Figure 5.3.7: 1 below):

• From signing the informed consent onwards through the Residual Effect period (REP), until trial completion, all AEs (serious and non-serious), and AESIs

• If in an individual patient only vital status information is collected from a certain time point on, no further AEs or AESIs will be reported for this patient

[figure not shown]

Figure 5.3.7: 1 Trial periods for collection of AEs

The REP is defined as 7 days after the last trial medication application, except for hypoglycaemia, where the REP is 1 day. All AEs which occurred through the treatment period and throughout the REP will be considered as on treatment (please see Section 7.3.4). Events which occurred after the REP will be considered as post-treatment events.

After the last per protocol contact the Investigator does not need to actively monitor patients for AEs. However, if the Investigator becomes aware of SAEs or AESIs that occurred after the last per protocol contact, the SAEs and AESIs should be reported by the Investigator to the Sponsor if considered relevant by the Investigator.

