# 3.3.4 Removal of patients from therapy or assessments

# 3.3.4.1 Removal of individual patients

An individual patient is to be withdrawn from trial treatment if:

- The patient withdraws consent for study treatment or study participation, without the need to justify the decision.
- The patient needs to start a restricted concomitant therapy (as listed in Section4.2) that, in the Investigator's opinion, poses a safety risk if taken as add-on to the trial medication
- The patient can no longer be treated with trial medication for other medical reasons (such as surgery, AEs, other diseases, or pregnancy)
- The patient experiences severe hypoglycaemia (for further details see Section 5.3.5.2) or repeated hypoglycaemic episodes or DKA that, in the Investigator's opinion, may put the patient at risk with continued participation

If a patient becomes pregnant during the trial the study medication will be stopped, the patient will be discontinued from the trial and the patient will be followed up until birth or otherwise termination of the pregnancy.

A patient can be discontinued after discussion between Sponsor and Investigator if eligibility criteria are being violated, or if the patient fails to comply with the protocol (e.g. non-attendance at study assessments).

Patients who drop out during the screening, T1DM therapy optimisation, or run-in periods prior to randomisation will be considered screening failures. They will be recorded as screening failures in the eCRF and no further follow-up is required. The data will be included in the trial database and will be reported.

Patients who discontinue the trial treatment or withdraw from the study after randomisation will be considered as "early discontinuations" and the reason for this premature discontinuation of the trial treatment or withdrawal from the study must be recorded in the eCRF. The data will be included in the trial database and will be reported.

For the analysis of this trial it is very important that assessments for each planned visit are still performed in accordance with the Flow Chart even if patients discontinue trial treatment. Patients who discontinue treatment prematurely will be followed up until the end of the study, unless they withdraw their consent for this to happen. All assessments related to the primary and key secondary endpoints still have to be performed as if the patient had remained

Page 35 of 144

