# 7.3.4 Safety analyses

Safety will be assessed for the endpoints listed in Section 5.1.3.2. All treated patients will be included in the safety evaluation (i.e. in the TS). Safety analyses will be mostly descriptive in nature and will be based on BI standards. In addition, statistical analysis for selected endpoints (to be defined in the TSAP) may be performed, if appropriate. No hypothesis testing is planned.

The active empagliflozin treatment groups will be compared with the placebo group in a descriptive way. Tabulations of frequencies/proportions will be used for the evaluation of

Page 85 of 144

Proprietary confidential information © 2017 Boehringer Ingelheim International GmbH or one or more of its affiliated companies

categorical (qualitative) data, and tabulations of descriptive statistics will be used to summarise continuous (quantitative) data.

Adverse events will be coded using the Medical Dictionary for Drug Regulatory Affairs (MedDRA). The analysis of AEs will be based on the concept of treatment emergent adverse events. That means that all AEs occurring from first study medication intake until 7 days after last study medication intake will be assigned to the randomised treatment. This includes AEs that start before first study medication intake and deteriorate under treatment. All AEs occurring before first study medication intake will be assigned to 'pre-treatment' and all AEs occurring after last study medication intake + 7 days will be assigned to 'post-treatment'. Additional listings based on actual treatment at onset of AE will be produced for patients who receive incorrect treatment at any point during the trial. Specific analyses of hypoglycaemia will assign events only up to the end of the last study medication intake + 1 day to the randomised treatment, later hypoglycaemia events will be assigned to 'post-treatment'.

Frequency, severity, and causal relationship of AEs will be tabulated by system organ class and preferred term after coding according to the current version of the MedDRA.

Independent of this rule, the relationship of an AE to the study medication will be assessed by the Investigator.

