7.8.1.1 Assignment of AEs to treatment

In general, the analysis of adverse events will be based on the concept of treatment emergent adverse events.

This means that all adverse events occurring between first drug intake until 7 days after last drug intake will be assigned to the randomised treatment. All adverse events occurring before first drug intake will be assigned to 'screening' and all adverse events occurring after last drug intake + 7 days will be assigned to 'post-treatment'. For details on the treatment definition, see [section 6.1](#).

For all adverse event analyses at week 26 except the specific analyses on hypoglycaemia (i.e. not the general hypoglycaemia AE analysis by SOC and PT), all adverse events with an onset date up to the minimum of (treatment stop + 7 days) and the week 26 cut-off date will be included. Events occurring after this date will be censored for the week 26 analysis. Refer to Section 6.1 for details on the week 26 cut-off date definition.

For the specific analyses on hypoglycaemia, the events with an onset date up to the minimum of (treatment stop + 1 day) and the week 26 cut-off date will be included.

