7.8.2 Laboratory data

For continuous safety laboratory parameters standardised and normalised values will be derived as well as the differences to baseline. The process of standardisation and normalisation as well as standard analyses for safety laboratory data are described in the BI guidance for the Display and Analysis of Laboratory Data ([10](#)). All analyses considering multiple of times upper limit of normal (ULN) will be based on original and not normalized data.

The analyses of laboratory data will be descriptive in nature and will be based on BI standards.

Results of laboratory analyses will be presented based on both SI units and US conventional units.

Baseline for safety laboratory parameters will be the last available measurement before the start of randomised study drug. In general, laboratory measurements taken up to 3 days after the last administration of randomised study drug will be considered as on-treatment. The exception will be for the liver enzyme elevation analysis (see below).

For all laboratory analyses at week 26, all laboratory parameters measured up to the minimum of (treatment stop + 3 days) and the week 26 cut-off date will be included. Laboratory measures observed after this date will be censored for the week 26 analysis. Refer to [section 6.1](#) for details on the week 26 cut-off date definition.

Only patients with at least one available on-treatment value will be included in the analysis of an individual laboratory parameter. All individual data will be presented in listings.

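### An amputation more than 7 days after the last dose leaves the on-treatment AESI count, even if the limb condition caused the drug stop; add a count over all follow-up

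*Protocol*

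**What the plan says.** Protocol 5.3.7 sets the residual effect period: "The REP is defined as 7 days after the last trial medication application, except for hypoglycaemia, where the REP is 1 day". What follows it is not counted as on treatment: "Events which occurred after the REP will be considered as post-treatment events". Protocol 7.3.4 repeats the rule for the safety analysis, with events "occurring after last study medication intake + 7 days will be assigned to 'post-treatment".

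SAP Table 6.7: 1 lists 7 days for adverse events and 1 day for hypoglycaemia, and has no row for amputation. SAP 7.8.1.1 introduces the 7-day rule as the general one. It then fixes the Week 26 scope as "For all adverse event analyses at week 26 except the specific analyses on hypoglycaemia" and the Week 26 window as "all adverse events with an onset date up to the minimum of (treatment stop + 7 days) and the week 26 cut-off date". Later events are censored from that analysis.

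Protocol 5.3.6.1 makes events involving lower limb amputation an AESI, covering amputation, disarticulation and auto-amputation. It asks for single reports: "Each lower limb amputation, disarticulation, or auto-amputation should be reported separately. The SAE report should include the date of the procedure". The condition that led to the procedure is a separate item in the same report. Protocol 5.1.3.2 defines the endpoint as the frequency of patients with AESIs up to 26 and 52 weeks of treatment.

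Protocol 3.3.4.1 includes surgery and adverse events among the reasons for withdrawing a patient from trial treatment. Protocol 5.3.7 and 6.2.3.4 keep adverse event collection going after drug stop, to Visit 16 at Week 52 for early discontinuers. It ends sooner if the patient withdraws or only vital status is being collected.

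**The concern.** Most adverse events start when the illness starts. This AESI is the procedure, and an infection or ischaemia of the limb can precede it by days or weeks. If that condition is why drug was stopped, the stop comes first and the 7-day clock may run out before the procedure takes place. The event then leaves the on-treatment count because of the illness that the AESI is meant to monitor. An exclusion of this kind can only lower the count.

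Amendment 2 added the AESI and gives new regulatory requirements as the reason. If few amputations occur, moving one or two of them to the post-treatment phase could change how the table reads.

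**Working it through.** The plan states no figure on this point, so there is none to reproduce. The check sets the rules side by side, then works out how much follow-up they leave outside the count.

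**1. Is the rule the same everywhere?** Yes, in the readable text. Protocol 5.3.7, protocol 7.3.4, SAP Table 6.7: 1 and SAP 7.8.1.1 all give last dose + 7 days for adverse events. The only exception is hypoglycaemia, whose window is shorter.

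**2. Does the Week 26 cut-off bring late events back?** No. For patients who stop early, SAP 6.1 defines the cut-off as the smaller of drug stop + X days and the Week 26 visit date (or Day 182). It is itself limited by drug stop.

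**3. Which patients are affected?** Those with a permanent stop and an onset more than 7 days after the last dose. SAP 6.1 runs the on-treatment period to the last intake plus the window, so an amputation during a temporary interruption stays on treatment if drug is restarted.

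**4. How much planned follow-up lies outside the window?** Planned end for an early discontinuer: 52 × 7 = Day 364. Share covered = 7 / (364 − stop day).

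| Drug stop | Days left to Day 364 | Covered | Not covered |
|---|---|---|---|
| Week 4 (Day 28) | 336 | 7 (2.1%) | 329 |
| Week 16 (Day 112) | 252 | 7 (2.8%) | 245 |
| Week 27 (Day 189) | 175 | 7 (4.0%) | 168 |
| Week 40 (Day 280) | 84 | 7 (8.3%) | 77 |

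For the Week 26 table, a stop at Week 16 leaves 182 − 112 = 70 days, of which 7 (10%) are covered.

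**5. Illustration on assumed inputs only.** The documents give neither an amputation rate nor a lag from drug stop to procedure.

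- *Lag.* If it is exponential with mean m days, P(lag > 7) = exp(−7/m). For m = 7, 14 and 28 this is 0.37, 0.61 and 0.78. These shares apply only to patients who stopped drug for the limb condition, and the size of that group is unknown.
- *Rate.* If it is 1 to 5 per 1000 patient-years, the two empagliflozin arms give at most 2 × 240 × 1 year = 480 patient-years, and 480 × 0.001 to 480 × 0.005 = 0.5 to 2.4 expected events. The 480 assumes that every patient completes 52 weeks of treatment.

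The two parts cannot be multiplied into an overall loss, because the share of amputations preceded by a limb-related drug stop is missing.

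**The case against.** The strongest reply is that the window fits the endpoint and the drug. The endpoint is framed as weeks of treatment. The protocol gives a terminal half-life of 12.4 hours (range 10 to 19) and a pharmacodynamic effect of about three days after the last dose. Seven days is 168 hours, or about 9 to 17 half-lives (168/19 to 168/10). A count to the end of follow-up answers a different question and takes in events long after exposure. This stands, and it is why the 7-day count should remain and not be replaced.

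Second, the safety information is not lost. Late events go to a defined post-treatment phase, and a limb infection or ischaemia that began on drug and ended treatment would appear in the on-treatment tables, including the one for adverse events leading to discontinuation. This also stands. It does not put the amputation itself into the AESI frequency.

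Third, the date that governs is open. The protocol asks for the procedure date in the report but does not say that it is the onset date, which SAP 7.8.1.1 uses. If a site dated the event from the underlying condition, it could still count. That is a reason to settle the date.

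A reader might infer more than the documents support:

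- *That the SAP plans no other amputation analysis.* SAP 7.8.1 names a lower limb amputation endpoint with its own collapsing rule, and the subsections between 7.8.1.3 and 7.8.2 are not public. Such an analysis cannot be called absent.
- *That the liver-enzyme exception in SAP 7.8.2 is a precedent for a longer window.* It departs from a 3-day laboratory window. Neither its length nor its direction is visible, so it should not be cited.
- *That the comparison between arms is biased.* The rule is the same in all arms, and no differential loss is shown. Protocol 7.3.4 plans no hypothesis test on safety.
- *That every excluded event is in the database.* Collection of adverse events stops at withdrawal, or once only vital status is recorded.

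**Conclusion.** The point holds in limited form. On the readable text, a lower limb amputation more than 7 days after a permanent drug stop is not counted under randomised treatment, even when the limb condition caused the stop. This is explicit for Week 26 and is the general rule for Week 52. The on-treatment frequency can therefore be biased low.

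The size of the bias cannot be derived from the documents. The day counts in the table follow from the planned schedule; the event and lag figures are assumptions. The conclusion also assumes that the procedure date is used as onset and that no unpublished SAP section sets a different window. It concerns a descriptive safety table and affects no confirmatory test. It supports a supplementary count, not a change of the main one.

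**What to change.** In SAP 7.8.1.1:

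- Keep the count to treatment stop + 7 days as it is.
- State that the procedure date is the onset date for lower limb amputation.
- Add a table, by randomised arm, of patients with a lower limb amputation from first dose to the end of individual follow-up, regardless of drug stop.
- Add a Week 26 version that runs to the Week 26 visit date or Day 182, without the drug-stop limit. Referring to the SAP 6.1 cut-off would not achieve this.
- If the non-public SAP text already contains such an analysis, confirm its window.

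The cost is a short addition to the SAP and one extra table from data already collected, with no change to trial conduct. The drawback is that the new table includes some events long after exposure; the retained 7-day count beside it shows how many.
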